1.1.3 Cross-over part (a subpart of cohort A-2)

Patients from Cohort A-2 who progress on isatuximab monotherapy may receive isatuximab plus REGN2810 at the discretion of the Investigators and if they still fulfill the eligibility criteria (except exclusion criteria #3 and #8). The screening period for the cross-over part is 28 days from progressive disease (PD) confirmation.

All screening processes for the patients in the Phase 1 and Phase 2 parts are to be conducted before combination IMP initiation for the cross-over part, except informed consent, demography, medical/surgical and disease history, and weight/height. Tumor biopsy at cross-over screening is required unless clinically unfeasible and after discussion with the Sanofi Medical Monitor. On treatment biopsy at Cycle 2, Day 1 (± 7 days) of the cross-over part is optional (fine needle aspirate is not acceptable). Patients who are included in the cross-over part should be evaluated as Cohort A-1 and Cohort B (except PK).

Patients who do not meet the cross-over part eligibility criteria should be followed up for safety and survival.

1.2 OBJECTIVES

1.2.1 Primary objectives

Phase 1:

- To characterize the safety and tolerability of isatuximab in combination with REGN2810 in patients with mCRPC who are naïve to anti-programmed cell death 1 (PD-1)/programmed cell death-ligand (PD-L1)-containing therapy naïve, or NSCLC who progressed on anti-PD-1/PD-L1-containing therapy, and to confirm the RP2D

Phase 2 (applicable to Cohorts A-1, A-2, B, C, and D):

- To assess the RR of isatuximab in combination with REGN2810 in patients with either mCRPC who are anti-PD-1/PD-L1 therapy naïve, or NSCLC who progressed on anti-PD-1/PD-L1 therapy, **or** of isatuximab as single agent in patients with mCRPC

1.2.2 Secondary objectives

- To evaluate the safety of the combination of isatuximab with REGN2810 or isatuximab monotherapy
- To evaluate the immunogenicity of isatuximab and REGN2810
- To characterize the PK profile of isatuximab single agent or in combination with REGN2810, and to characterize the PK of REGN2810 in combination with isatuximab
- To assess overall efficacy of isatuximab in combination with REGN2810 or single agent (tumor burden change, duration of response [DOR], and progression-free survival [PFS])

1.3 DETERMINATION OF SAMPLE SIZE

Phase 1

In Phase 1, approximately 6 (assuming 6 patients for the starting dose) to 24 (assuming 12 patients for the starting dose plus 12 patients for DL-1) DLT evaluable patients are expected to be enrolled. The actual sample size will vary depending on DLTs observed and the number of dose levels explored. Patients who are not evaluable for DLT assessment in the Phase 1 part may be replaced.

Phase 2

The Phase 2 part of the study is to evaluate initial anti-tumor activity based on tumor response using response evaluation criteria in solid tumors (RECIST) 1.1 criteria (1) for NSCLC and prostate cancer clinical trials working group 3 (PCWG3) criteria (2) for mCRPC. The efficacy evaluation is based on Simon's 2 stage designs with 90% power at 5% 1-sided alpha level for each of the patient cohorts of mCRPC and NSCLC patients, respectively. The assumption of RR, the required sample sizes and the number of responders at each stage are provided in [Table 2](#).

Table 2 - Sample size calculation

Indication	H0	H1	Sample size	Number (%) of required responses	
			Stage 1	Final	Stage 1
mCRPC (Combo)	10%	26%	23	49	≥3 (13.0%)
mCRPC (Single)	10%	26%	20	36	≥2 (10.0%)
NSCLC (Combo)	5%	22%	20	36	≥2 (10.0%)
					≥5 (13.9%)

Abbreviations: H0=null hypothesis; H1=alternative hypothesis; mCRPC=metastatic, castration-resistant prostate cancer; NSCLC=non-small cell lung cancer.

Note: Based on the number of objective responses and the totality of data observed within a treatment cohort in Phase 2 Stage 1, the Sponsor may decide to advance such a treatment cohort to Phase 2 Stage 2 after consulting with Investigators.

Patients who received the recommended dose regimen in Phase 1 will be also included in the Phase 2 Stage 1 (eg, if 6 NSCLC patients were enrolled in Phase 1, only 14 NSCLC patients will be needed to complete the Phase 2 Stage 1 NSCLC cohort).

In Phase 2, approximately 134 patients are expected to be enrolled (assuming Cohort A-1, A-2 and B complete 2 stages), including approximately 66 patients in Phase 2 Stage 1 and approximately 68 patients in Phase 2 Stage 2. The patients who are treated with RP2D in the Phase 1 part will be counted as Phase 2 part patients. If isatuximab 10 mg/kg Q3W in combination with REGN2810 or monotherapy without the isatuximab 10 mg/kg QW for 3 weeks is to be tested in a mCRPC or NSCLC cohort, 49 or 36 additional patients will be needed, respectively.

The isatuximab monotherapy cohort (Cohort A-2) will be initiated when the initial anti-tumor activity of isatuximab combination therapy is observed in the Phase 2 Stage 1 according to the study design. When an isatuximab monotherapy cohort (Cohort A-2) is initiated, patients with mCRPC will be randomly assigned in a 1:1 randomization to either the isatuximab in combination with REGN2810 (Cohort A-1) or the isatuximab monotherapy (Cohort A-2). The purpose of the randomization is to avoid the potential bias of patient assignment, and is not to compare between 2 cohorts. Randomization will end when 1 of the 2 cohorts completes the enrollment.

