#### Phase 2 part

The Phase 2 part of the study is to evaluate initial anti-tumor activity based on tumor response using RECIST 1.1 criteria for NSCLC and PCWG3 criteria for mCRPC. The efficacy evaluation is based on Simon's 2-stage design with 90% power at 5% 1-sided alpha level for each of the patient cohorts of mCRPC and NSCLC patients respectively.

The assumption of RR, the required sample sizes, and the number of responders at each stage are provided below:

Indication	H₀	H 1	Sample size		Number (%) of responses to reject H		
			Stage 1	Final	Stage 1	Final	
mCRPC (Combo)	10%	26%	23	49	≥3 (13.0%)	≥9 (18.4%)	
mCRPC (Single)	10%	26%	23	49	≥3 (13.0%)	≥9 (18.4%)	
NSCLC (Combo)	5%	22%	20	36	≥2 (10.0%)	≥5 (13.9%)	

Abbreviations: H₀=null hypothesis; H₁=alternative hypothesis; mCRPC=metastatic, castration-resistant prostate cancer; NSCLC=non-small cell lung cancer.

Note: Based on the number of objective responses and the totality of data observed within a treatment cohort in Phase 2 Stage 1, the Sponsor may decide to advance such a treatment cohort to Phase 2 Stage 2 after consulting with Investigators.

Patients who received the RP2D in Phase 1 will be also included in Phase 2 Stage 1 (eg, if 6 NSCLC patients were enrolled in Phase 1, only 14 NSCLC patients will be needed to complete the Phase 2 Stage 1 NSCLC cohort).

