1.5 MODIFICATIONS TO THE STATISTICAL SECTION OF THE PROTOCOL

Not applicable.

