3 INTERIM ANALYSIS (IA)

An IA will be performed for each cohort after the first 23 patients for mCRPC cohorts or the first 20 patients for NSCLC cohorts in the Phase 2 part have completed 6 cycles. The interim analysis may be conducted earlier if the required number of responders proceeding to Phase 2 Stage 2 is achieved.

The analysis will include the following parameters/analyses (defined in [Section 2.1](#)): response rate, demographics and baseline characteristics, prior or concomitant medication, AEs (TEAE, death, SAE, TEAE leading to discontinuation, IAR, AESI), and laboratory variables (abnormality of hematological and chemistry test). If needed, more data will be analyzed to inform the futility decision including additional efficacy, PK, and biomarker.

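### As extracted, SAP Table 2 gives the isatuximab monotherapy mCRPC cohort the NSCLC design (20/36, at least 2 responses), in conflict with the protocol and the rest of the SAP; check the source PDF and, if confirmed, restore 23/49.

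*SAP*

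**What the plan says.** SAP section 1.3 claims "Simon's 2 stage designs with 90% power at 5% 1-sided alpha level for each of the patient cohorts". Its Table 2 then shows, as extracted:

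- combination mCRPC: "mCRPC (Combo) 10% 26% 23 49 ≥3 (13.0"
- monotherapy mCRPC (Cohort A-2): "mCRPC (Single) 10% 26% 20 36 ≥2 (10.0"
- combination NSCLC: "NSCLC (Combo) 5% 22% 20 36 ≥2 (10.0"

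The monotherapy row has the mCRPC hypotheses but the NSCLC sample sizes and Stage 1 cut-off.

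Other statements of the Cohort A-2 design differ:

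- The protocol synopsis (sample size, Phase 2 part) has "mCRPC (Single) 10% 26% 23 49 ≥3 (13.0%) ≥9 (18.4". Protocol section 13.1, Table 8, carries the same values.
- Under its own Table 2, SAP section 1.3 expects about 134 Phase 2 patients, "including approximately 66 patients in Phase 2 Stage 1 and approximately 68 patients in Phase 2 Stage 2".
- SAP section 3 states: "An IA will be performed for each cohort after the first 23 patients for mCRPC cohorts".
- SAP section 1.5, which would record changes to the protocol's statistical section, says "Not applicable".

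**The concern.** The Table 2 row fixes when Cohort A-2 is assessed, how many responses count as enough to consider Stage 2, and how large the cohort becomes. A 20/36 design built for 5% versus 22% will not have the same error rates at 10% versus 26%. If the row really is printed this way, the SAP claims an alpha and power that its own design for this cohort cannot deliver. The SAP and the protocol would also give different Stage 1 counts for the same cohort, 2 of 20 against 3 of 23, and the SAP records no change that would explain the difference.

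**Working it through.** **Inputs.** H0 = 10% and H1 = 26% for mCRPC; one-sided alpha 5%; power 90% (SAP 1.3, protocol 13.1). Protocol row: 23 in Stage 1, 49 in total, at least 3 then at least 9 responses. SAP row as extracted: 20 in Stage 1, 36 in total, at least 2 responses; no final cut-off is legible.

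**Formula.** For Stage 1 size n1, Stage 1 cut-off a, total N and final cut-off r, at response rate p:

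P(success) = sum over x1 ≥ a of P(X1 = x1) × P(X2 ≥ r − x1), with X1 ~ Bin(n1, p) and X2 ~ Bin(N − n1, p).

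Alpha is this at H0, power is this at H1.

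**Step 1: reproduce the plan's own designs.**

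- Protocol mCRPC, 23/49, at least 3 then 9, at 10%/26%: alpha 0.0479, power 0.9015.
- NSCLC, 20/36, at least 2 then 5, at 5%/22%: alpha 0.0294, power 0.9018.

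Both meet the stated 5% and 90%, so the method matches the plan's.

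**Step 2: Stage 1 count at a true rate of 10%.**

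- SAP row: P(X ≥ 2 of 20) = 1 − 0.9^20 − 20(0.1)(0.9^19) = 1 − 0.1216 − 0.2702 = 0.608.
- Protocol row: P(X ≥ 3 of 23) = 1 − 0.9^23 − 23(0.1)(0.9^22) − 253(0.01)(0.9^21) = 1 − 0.0886 − 0.2265 − 0.2768 = 0.408.

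**Step 3: every plausible final cut-off for 20/36 with at least 2 in Stage 1.**

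| Final cut-off of 36 | Alpha (10%) | Power (26%) |
|---|---|---|
| at least 5 | 0.269 | 0.963 |
| at least 6 | 0.140 | 0.928 |
| at least 7 | 0.062 | 0.859 |
| at least 8 | 0.023 | 0.753 |
| at least 9 | 0.008 | 0.617 |

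The lowest cut-off that holds alpha at or below 5% is 8, with power 0.753. The highest that keeps 90% power is 6, with alpha 0.140. A search over other Stage 1 cut-offs and other Stage 1 sizes with 36 in total found no design meeting both. The illegible final cut-off therefore cannot rescue the row.

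**Step 4: totals for Cohorts A-1, A-2 and B.**

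| | SAP text | A-2 at 23/49 | A-2 at 20/36 |
|---|---|---|---|
| Phase 2 | 134 | 49+49+36 = 134 | 49+36+36 = 121 |
| Stage 1 | 66 | 23+23+20 = 66 | 23+20+20 = 63 |
| Stage 2 | 68 | 26+26+16 = 68 | 26+16+16 = 58 |

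The protocol row reproduces all three totals exactly; the SAP row reproduces none.

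**The case against.** The strongest objection is that the row may not be in the SAP at all. Table 2 is plainly broken in the extracted text: both mCRPC rows have lost their final cut-off, and the NSCLC final cut-off (at least 5, 13.9%) sits alone on a separate line. The suspect row matches the row below it in all three design fields, which misaligned cells or an author's copying slip could equally produce. That 2/20 equals 10.0% does not separate the two explanations. This objection stands, and it is why the finding depends on the PDF. For the same reason, the missing final cut-off should not be counted as an omission.

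A second objection is that the trial would be run on 23/49 in any case, since the protocol, the SAP totals and the SAP interim all say so. Protocol section 13.4.4.1 also ties the final test to protocol section 13.1. This largely stands. It makes a clerical slip or an extraction fault the only plausible explanations, but it does not justify leaving a wrong row in the SAP.

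A reader might infer that an inactive drug would advance 61% of the time. The documents do not support that. The figure applies only if this one row were followed against the SAP's own interim trigger. Meeting the count does not trigger Stage 2 either: the note to Table 2 leaves the decision to the sponsor on the totality of data, and SAP section 3 allows further efficacy, PK and biomarker data to inform futility. Cohort A-2 also opens only if Cohort A-1 proceeds to Stage 2.

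A reader might also infer that the cohort was redesigned, or that two rules were left open to choose between once data are seen. Nothing shows either. SAP 1.5 declares no change, and only the protocol gives a complete legible rule.

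**Conclusion.** The inconsistency is real in the text as supplied. The mCRPC (Single) row of SAP Table 2 disagrees with the protocol, with the SAP's own totals, with its 23-patient mCRPC interim and with its declaration of no modification.

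If the source PDF confirms the row, the stated 5% alpha and 90% power cannot be met for Cohort A-2 at any final cut-off. The chance of meeting the Stage 1 count at a true 10% rate would be 0.61, against 0.41 under the protocol row. These figures assume that the row is applied literally, that responses are independent with a common rate, and that success requires both the Stage 1 and the final count.

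If the PDF shows 23/49, there is no error. Either way, this is a one-row consistency correction conditional on the PDF check, not evidence that the planned design is unsound: the protocol design meets its stated error rates.

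**What to change.** 1. Check the mCRPC (Single) row of Table 2 in the source PDF of the SAP. If it shows 23/49, no change is needed.
2. If it shows 20/36, restore the protocol Table 8 values: 23 in Stage 1, 49 in total, at least 3 responses (13.0%) in Stage 1 and at least 9 (18.4%) at the final analysis.
3. Add one sentence stating that this row governs the Cohort A-2 interim and final assessments.

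The cost is one table row and one sentence. No patients are added to the planned 134. The SAP's totals and its mCRPC interim trigger already assume these values and stay as they are.

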1.4 STUDY PLAN

The complete study plan is presented in section 1.1 of the protocol.

1.5 MODIFICATIONS TO THE STATISTICAL SECTION OF THE PROTOCOL

Not applicable.

1.6 STATISTICAL MODIFICATIONS MADE IN THE STATISTICAL ANALYSIS PLAN

Not applicable. This is not an amended statistical analysis plan (SAP).

2 STATISTICAL AND ANALYTICAL PROCEDURES

Patients treated at the RP2D in Phase 1 will be included in the analysis with patients of the same tumor type in Phase 2. If the RP2D is the starting dose, all data from the patients in phase 1 will be summarized together with the data from the patients of the same tumor type in Phase 2 except for the DLT analysis.

Data from mCRPC and NSCLC cohorts in the Phase 2 part will be analyzed and reported separately by cohort. Data from the cohort A-2 cross-over part will be summarized separately unless otherwise noted.

2.1 ANALYSIS ENDPOINTS

2.1.1 Demographic and baseline characteristics

The baseline value is defined as the last assessment for this parameter before first administration of study treatments unless otherwise noted.

All baseline safety and efficacy parameters (apart from those listed below) will be presented along with summary statistics in the safety and efficacy sections ([Section 2.4.5](#) and [Section 2.4.6](#)).

Demographic characteristics

Demographic variables include race (American Indian or Alaska Native, Asian, Black or African American, Native Hawaiian or Other Pacific Islander, White, Not reported, Unknown), ethnicity (Hispanic or Latino, Not Hispanic or Latino, Not reported, Unknown), age in years, weight (kg), height (cm) and eastern cooperative oncology group (ECOG) performance status at baseline.

Medical or surgical history

Medical or surgical history includes relevant history of previous or associated pathologies other than the tumor.

This information will be coded using the version of Medical Dictionary for Regulatory Activities (MedDRA) currently in effect at Sanofi at the time of database lock.

Disease characteristics at diagnosis

The following disease characteristics at initial diagnosis will be described:

- Time from initial diagnosis to first study treatment administration (in years)
- Histology (diagnosis as collected in electronic case report form (eCRF))
- Disease Location
- Histopathology type (as collected in eCRF)

- Stage of the disease (as collected in eCRF)
- Gleason Score (for patients with mCRPC)

Disease characteristics at study entry - mCRPC

The following disease characteristics at study entry will be described:

- Disease extent (metastatic, Loco Regional Recurrence, Primary, locally advanced)
- Criteria for progression (prostate-specific antigen (PSA), soft tissue, bone metastasis)
- Baseline PSA

Disease characteristics at study entry - NSCLC

Disease extent (metastatic, Loco Regional Recurrence, Primary, locally advanced) will be summarized.

Prior anticancer therapies

Prior anti-cancer treatments are collected by regimen in the eCRF. The following variables will be summarized:

- Prior chemotherapy (by category: 0, 1, 2, 3 or more regimens): Number (%) of patients who received Taxane chemotherapy will be summarized for mCRPC cohorts
- Number of prior regimens (by category: 1, 2, 3, >3)
- Prior radiation therapy: number (%) of patients with any prior radiotherapy related to mCRPC or NSCLC by intent
- Prior surgery: number (%) of patients with any prior surgery related to mCRPC or NSCLC by type of procedure (Preferred Term)

In addition, for mCRPC cohorts, prior hormonal therapy will be summarized by category (1, 2, 3 or more regimens). Number (%) of patients who received enzalutamide only, abiraterone only and enzalutamide + abiraterone will be summarized.

For NSCLC cohort, number (%) of patients who received anti-PD1/PDL-1 containing regimen will be summarized by category (1, 2 or more regimens).

2.1.2 Prior or concomitant medications (other than anticancer therapies)

All medications will be coded using the World Health Organization-Drug Dictionary (WHO-DD), using the version currently in effect at Sanofi at the time of database lock.

- Prior medications are those the patient used prior to first study treatment administration. Prior medications can be discontinued before first dosing or can be ongoing during treatment phase

- Concomitant medications are any treatments received by the patient concomitantly to the study treatment from first administration to the last administration + 30 days. A given medication can be classified both as a prior medication and as a concomitant medication
- Post-treatment medications are those the patient took in the period running from the day after the last study treatment administration + 30 days up to the end of the study

Infusion associated reaction (IAR) medications

As defined in Section 8.2 of the study protocol, patients were to routinely receive premedications prior to isatuximab infusion to reduce the risk and severity of hypersensitivity reactions commonly associated with monoclonal antibodies. Premedications are defined in the protocol as non-investigational medicinal product(s). Premedications are reported on a specific eCRF page.

Any technical details related to computation, dates, imputation for missing dates are described in [Section 2.5](#).

2.1.3 Efficacy endpoints

2.1.3.1 Primary efficacy endpoint(s)

The primary efficacy endpoint for the Phase 2 part of the study is RR.

For patients with NSCLC, the RR is defined as the proportion of patients achieving complete response (CR) or partial response (PR) as best overall response (BOR), assessed by the investigator per RECIST 1.1 criteria, relative to the total number of patients in the analysis population. The confirmation of complete or partial response is required to determine BOR. BOR will be derived per RECIST 1.1 criteria using disease assessments performed from the first dose of treatment through the study excluding any assessments performed after the cutoff date or following the initiation of a further anticancer treatment. Clinical deterioration will not be considered as progression in the primary analysis of RR.

For patients with mCRPC, response will be defined by radiographic objective response (achieving CR or PR as BOR for soft tissue) assessed and confirmed by the Investigators and/or a PSA decline of $\geq 50\%$ from baseline that is subsequently confirmed per PCWG3 criteria (protocol Appendix A). The PSA decline must be confirmed to be sustained by a second PSA value obtained 4 or more weeks later. BOR for soft tissue will be Non-CR/Non-PD for patients with no baseline target and non-target lesions identified at baseline and no new lesions reported in post-baseline tumor assessments.

2.1.3.2 Secondary efficacy endpoint(s)

The secondary efficacy endpoints are:

- Tumor burden change: Tumor burden change is defined as the best percent-change from baseline in a sum of the diameters (longest for non-nodal lesion, short axis for nodal lesions) for all target lesions

Area under the curve (AUC) of percent-change from baseline in tumor burden is defined as the area under the percent-change from baseline versus time curve calculated using the trapezoidal method from the date of the first post-baseline assessment to the date of the last assessment

The time-adjusted AUC of percent-change from baseline in tumor burden is defined as AUC of percent-change from baseline in tumor burden divided by the duration of the assessment

- Duration of response: Duration of response is defined as the time from the date of first response (PR or CR in radiographic objective response, or PSA decline $\geq 50\%$ for patients with mCRPC) that is subsequently confirmed to the date of first disease progression or death, whichever occurs first. Disease progression includes radiographic disease progression or unequivocal clinical progression. The RECIST 1.1 criteria will be followed for assessment of radiographic disease progression in patients with NSCLC and the PCWG3 criteria will be followed in patients with mCRPC. For patients with mCRPC, radiographic progression includes progression by PCWG3 modified RECIST 1.1 for soft tissue and/or PCWG3 defined progression by bone scan. In the absence of disease progression or death before the analysis cut-off date or the date of initiation of a further anticancer treatment, the DOR will be censored at the date of the last valid response assessment not showing disease progression performed prior to initiation of a further anticancer treatment and the analysis cut-off date, whichever is earlier. DOR will not be calculated for patients who do not achieve a response
- Progression-free survival: For mCRPC patients, PFS is defined as the time from first study treatment administration to the date of first documented disease progression or the date of death from any cause, whichever occurs first. Disease progression includes radiographic disease progression (per PCWG3 criteria) or unequivocal clinical progression. For NSCLC patients, PFS is defined as the time from first study treatment administration to the date of first documented radiographic progression (per RECIST 1.1) or the date of death from any cause, whichever occurs first

For patients who did not experience documented disease/radiographic progression or death before the analysis cut-off date or the date of initiation of new anticancer treatment, PFS will be censored at the date of the last valid disease/radiographic assessment not showing disease progression performed prior to initiation of a further anticancer treatment or the analysis cut-off date, whichever comes first. In addition, patient without PFS event (death or documented disease/radiographic progression) and without any valid post-baseline disease assessments will be censored at the day of first treatment (Day 1)

- Disease control rate (DCR): DCR is defined as the proportion of patients with confirmed complete response (CR) or partial response (PR) or stable disease (SD), as assessed by Investigator (per PCWG3 criteria for mCRPC patients and per RECIST 1.1 criteria for NSCLC patients) relative to the total number of patients in the analysis population

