- x Immunophenotyping: a sample of peripheral blood will be drawn at Cycle 1 Day 1, Cycle 2 Day 1 and Cycle 3 Day 1 and then on Day 1 prior to IMP administration of each odd cycle starting from Cycle 5 (eg Cycle 5, Cycle 7, Cycle 9, Cycle 11, etc), at the EOT visit, and at follow-up (60 days after last IMP administration).
- y Plasma or serum cytokine concentration: A sample of peripheral blood will be drawn at baseline and Cycle 1 Day 1, Cycle 2 Day 1, Cycle 3 Day 1 and then on Day 1 prior to IMP administration at each odd cycle starting from Cycle 5 (ie, Cycle 5, Cycle 7, Cycle 9, Cycle 11 etc), at the EOT visit and at follow-up (60 days after last IMP administration).
- z Tumor assessment: CT or MRI of the chest, abdomen, pelvis and any other locations with suspicion or evidence of disease involvement is to be performed in all patients at screening (diagnostic quality scans performed as part of routine clinical management within 28 days prior to IMP initiation are acceptable). Repeat every 9 weeks starting at the end of Cycle 3 (63 ±7 days; disease assessment timing should follow calendar days and should not be adjusted for delays in cycle start), whenever disease progression is suspected, at the EOT visit (if not performed in the past 30 days) and during follow-up (if discontinue IMP without PD, repeat every 90 days), using the same method for each assessment. If tumor assessment status is partial or complete response, changes in tumor measurements must be confirmed by repeat assessments that should be performed no less than 4 weeks after the criteria for response are first met. Initial evidence of progression should be confirmed no less than 4 weeks later, see Section 6.7.1. Tumor assessment is not needed for patients who start another anti-cancer treatment regimen. Study sites must retain disease assessment images, as Sponsor may decide to collect these images for possible Independent Central Review in the future.

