# 9.6.2 Secondary endpoints

Secondary efficacy endpoints are:

- Tumor burden change: defined as the best percent-change from baseline in a sum of the diameters (longest for non-nodal lesion, short axis for nodal lesions) for all target lesions. In addition, the area under the curve (AUC) and the time-adjusted AUC of percent-change from baseline in a sum of the diameter for all target lesions will also be summarized in an exploratory fashion.
- Duration of response: defined as the time from the date of first response (PR or CR in radiographic objective response, or PSA decline ≥50% for patients with mCRPC) that is subsequently confirmed to the date of first disease progression or death, whichever occurs first. The RECIST 1.1 criteria (Appendix B) will be followed for assessment of tumor response in patients with NSCLC and the PCWG3 criteria (Appendix A) will be followed for the assessment of tumor response in patients with mCRPC. Disease progression includes radiographic disease progression or unequivocal clinical progression. For patients with mCRPC, radiographic progression includes progression by PCWG3 modified RECIST 1.1 for soft tissue and/or PCWG3 defined progression by bone scan. In the absence of disease progression or death before the analysis cut-off date or the date of initiation of a further anticancer treatment, the DOR will be censored at the date of the last valid response assessment not showing disease progression performed prior to initiation of a further anticancer treatment and the analysis cut-off date, whichever is earlier. DOR will not be calculated for patients who do not achieve a response.
- Progression-free survival: defined as the time from first study treatment administration to the date of first documentation of PD (RECIST 1.1 for patients with NSCLC and PCWG3 criteria for patients with mCRPC) or the date of death from any cause. The same censoring rules as DOR will be used.
- Disease control rate (DCR): defined as the proportion of patients with confirmed complete response (CR) or partial response (PR) or stable disease (SD), as assessed by Investigator relative to the total number of patients in the analysis population.

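### The tumour-burden AUC starts at the first post-baseline scan, so a patient with only one such scan scores zero or undefined whatever the tumour did

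*SAP*

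**What the plan says.** Protocol 9.6.2 makes best percent-change in the sum of target-lesion diameters the secondary endpoint. It adds, as exploratory summaries, the AUC and "the time-adjusted AUC of percent-change from baseline in a sum of the diameter for all target lesions". It gives no start or end point for the area.

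The window is set only in SAP 2.1.3.2. The trapezoidal area runs "from the date of the first post-baseline assessment to the date of the last assessment". The time-adjusted version is "AUC of percent-change from baseline in tumor burden divided by the duration of the assessment", and that duration has no stated start or end date.

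The scan schedule is in the tumour-assessment footnote of Protocol 1.3:
- "Repeat every 9 weeks starting at the end of Cycle 3 (63 ±7 days", so the first post-baseline scan falls at about day 63.
- "Initial evidence of progression should be confirmed no less than 4 weeks later".
- A scan is due "at the EOT visit (if not performed in the past 30 days").
- "Tumor assessment is not needed for patients who start another anti-cancer treatment regimen".

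No rule covers a patient with one post-baseline scan. SAP 2.5.2, on data handling for secondary efficacy variables, is marked as not applicable. SAP 2.5.3 bases summaries on observed data only.

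**The concern.** The baseline point is known for every patient with measurable disease, since percent-change there is 0%. The SAP nevertheless leaves it out of the trapezoid. When there is only one post-baseline scan, the first and last assessments are the same date and the window has zero length. The rule then returns a fixed value, or none, instead of one that reflects the observed change.

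A raw AUC of zero cannot be told apart from no change in tumour burden. An undefined time-adjusted AUC drops out under the observed-data rule, or forces the programmer to improvise. Whether a patient has one scan or several is plausibly related to outcome, so this is not obviously a harmless loss.

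**Working it through.** The plan states no figure for the AUC, so there is none to reproduce. The check applies the SAP's trapezoid, the sum of (t[i+1] − t[i]) × (y[i] + y[i+1]) / 2, to illustrative patients. It does so first over the SAP window and then from baseline (time 0, change 0%). Scan days follow the 9-week schedule; the tumour changes are assumed. The baseline scan is taken as day 0.

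**1. One scan, +40% at day 63.**
- SAP window: length 63 − 63 = 0, so AUC = 0. Time-adjusted: 0/0 if the divisor is the same window; 0/63 = 0 if it runs from baseline.
- From baseline: 0.5 × 63 × 40 = 1260 %-days; 1260/63 = +20%.

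**2. Responder, −30% at day 63 and −40% at day 126.**
- SAP window: 63 × (−35) = −2205; −2205/63 = −35%.
- From baseline: 0.5 × 63 × (−30) = −945; −945 − 2205 = −3150; −3150/126 = −25%.

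**3. Progressor with a confirmation scan, +40% at day 63 and +60% at day 91.**
- SAP window: 28 × 50 = 1400; 1400/28 = +50%.
- From baseline: 1260 + 1400 = 2660; 2660/91 = +29.2%.

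In cases 2 and 3 the time-adjusted value lies further from zero under the SAP window, in whichever direction the tumour moved. The raw AUC is nearer zero, because the first interval is missing.

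**4. Sensitivity to the baseline scan date.** Protocol 1.3 accepts a CT/MRI up to 28 days before first dose. If day 63 is counted from first dose and the scan was 28 days earlier, the first interval is 63 + 28 = 91 days.
- Case 1: 0.5 × 91 × 40 = 1820 %-days, still +20% time-adjusted.
- Case 2: 0.5 × 91 × (−30) = −1365; (−1365 − 2205)/154 = −23.2%.

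**5. Who has one scan.** SAP 2.4.5 sets the cut-off for secondary efficacy endpoints at 12 months after the last patient's first treatment. That leaves room for scheduled scans at days 63, 126, 189, 252 and 315, so the cut-off itself does not create one-scan patients. Early stopping can: the end-of-treatment scan is waived if one is recent, and scanning is not needed once a new regimen starts.

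**6. Cohort effect under assumed shares.** Take 20% responders with five scans (−30%, then −50% four times): −47.5% time-adjusted under the SAP window, −41% from baseline. A share f has one scan at +40%. The rest are stable with three scans (0, +5, +20%): +7.5% and +5%.
- f = 0: SAP window 0.2 × (−47.5) + 0.8 × 7.5 = −3.5; from baseline 0.2 × (−41) + 0.8 × 5 = −4.2.
- f = 20%, undefined values dropped: SAP window (−9.5 + 0.6 × 7.5)/0.8 = −6.25; from baseline −8.2 + 0.6 × 5 + 0.2 × 20 = −1.2.

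The SAP window gives the less favourable mean at f = 0 and the more favourable mean at f = 20%.

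**The case against.** The strongest reply is that little depends on this. Protocol 13.4.4.2 and SAP 2.4.5.2 label the AUC summaries exploratory and place them with an analysis of patients who have measurable disease. Best percent-change, the actual secondary endpoint, includes one-scan patients at their true value and is shown graphically. That stands, and it makes this a minor point.

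Second, 0/0 depends on reading the undefined divisor as the AUC window. That is the natural reading but not the only one. Counted from baseline, the value is 0, which is still not the observed change. If the value is undefined, the number of available data that SAP 2.4 reports would reveal the loss. It would not reveal the raw AUCs set to zero.

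Third, averaging only observed post-baseline change is a defensible description when there are two or more scans. That also stands: for those patients the choice of window is partly preference.

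Fourth, a reader might infer that the patients lost are mainly early progressors. The documents do not establish this. Progression should be confirmed by a scan at least 4 weeks later, and clinically stable patients may stay on treatment until then, so many early progressors would have two scans. Patients who stop without progression are to be scanned every 90 days. The affected group is those who stop without a confirmation or later scan; early stoppers are the likely source, but no share is given.

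**Conclusion.** The rule as written returns an uninformative value for any patient with one post-baseline scan: raw AUC 0, and time-adjusted AUC 0/0 or 0 depending on how the divisor is read. A +40% change at day 63 becomes 0 instead of 1260 %-days (+20% time-adjusted). The zero raw AUC follows directly from the SAP text; the from-baseline comparison assumes the baseline scan is day 0 and a linear path to the first scan.

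Two stronger conclusions are tempting and not supported. One is that the cohort summary is tilted in the treatment's favour: the illustration changes direction with the assumed share of one-scan progressors, and the documents give no share. The other is that responders are overstated. In the example that holds only for the time-adjusted AUC (−35% against −25%); the raw AUC is understated (−2205 against −3150 %-days), and a progressor with two scans is inflated too (+50% against +29.2%).

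The consequence is confined to an exploratory summary. Response rate, best percent-change, DOR and PFS do not use this window.

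**What to change.** In SAP 2.1.3.2, compute the AUC from the baseline scan (change 0%) to the last assessment, and define the divisor of the time-adjusted AUC as the time from the baseline scan to the last assessment. Naming the baseline scan date as time zero also settles the gap of up to 28 days before first dose. Report the number of patients with zero and with one post-baseline scan beside the summary; those with none are missing under either window.

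The cost is a small wording change in the SAP and one line in a table. No new data are needed, and because the protocol sets no window, its text does not conflict with the change.

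There is a small downside. The change assumes a linear path over the unobserved first 9 weeks, and short follow-up still pulls the score towards zero. One scan at +40% gives +20%, while +40% held over five scans gives (1260 + 40 × 252)/315 = +36%.
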